16. PRIVACY AND CONFIDENTIALITY CONSIDERATIONS INCLUDING DATA ACCESS AND MANAGEMENT

Study recruitment and enrollment will be monitored through a Screening/Enrollment Log, both created as password protected Microsoft Excel spreadsheets.

The Screening/Enrollment Log will include a participant's: name source of contact (community vs. clinic), age, diagnosis (spinal pathology and date), gender, ethnicity, current drug regimen (i.e. mostly focused on opiate usage), handedness and meditation experience. The Screening/Enrollment Log will provide dates corresponding to when informed consent was obtained, the identified 2-point VAS increase angle/height (from the straight leg raise test), height and weight on the day of the screening/session 1, confirmed eligibility, as well as a note section for miscellaneous notations. This information will be obtained from a phone screening and their responses will be logged into the spreadsheet, where a judgment will be made regarding their suitability for entry into the study according to study eligibility criteria.

The Screening/Enrollment Log will be analyzed in the interim between cohorts to determine which input stream (community vs. clinical) yields the highest percentage of input to the study. This analysis may prove useful for future tweaks of our recruiting strategies. We will also look at the stream sourcing with respect to cohort diversity. Whenever possible, we will seek to maximize ethnic and socioeconomic diversity in order to broaden the implications of the study's results. The

No identifying information will be used on any study documents after enrollment. Enrolled participants will be assigned a unique subject identification number (SID) that will be used on all CRFs and study related documents after enrollment. The SID will be linked to participant identifiable information (as described in item 9) in a separate Subject Identification Log, created and password protected in a Microsoft excel spreadsheet. This will be stored on the coordinator's password protected and encrypted computer on the 3rd floor of the ACTRI.

All completed case report forms (CRF), created for all study related visit requirements, will kept in a study binder at a central and secure location in our facility to better facilitate the tracking of each enrolled participant and cohort. All study related documents with corresponding SIDs will be stored in

a folder, in a larger cohort binder that's divided by each individual participant. Each participant's binder will be monitored periodically (monthly) to ensure subject's progress through the study as well as positive or negative progression of symptoms of interest. All study-related safety and adverse events will be reported to the UCSD Institutional Review Board (IRB) and IMC per appropriate reporting timeframes. All study-related records/information will be made available to the UCSD IRB and IMC at any time of their choosing.

All study data will be processed in a HIPPA-compliant fashion to ensure confidentiality and to protect the PHI collected from improper use and/or disclosure. Digital data will be stored on both physically and software protected computers and will only be accessed by study personnel from within the ACTRI building (coordinator computer). Any reference to individual subjects in reports of this work will utilize a study identification number (SID) to preserve confidentiality.

Following data collection participant identifying information will be destroyed when data collection and corresponding statistical analyses for the primary aims are completed, consistent with data validation and study design, producing an anonymous analytical data set. When these are complete, the study coordinator(s) or PI will shred any and all physical documents containing any identifiers/PHI on it. Our primary aim is to ensure participant safety and confidentiality; thus, we will take the highest measures and uphold the most stringent standards to ensure patient confidentiality.

17. POTENTIAL BENEFITS

This research is not expected to directly benefit individual participants, but is likely to yield generalizable knowledge. The basic understanding of how mind body approaches function to alleviate pain and improve wellbeing are unknown. The primary purpose of the proposed study is to determine if endogenous opioidergic systems are engaged by mindfulness meditation to reduce chronic low back pain. This work will also inform whether or not mind body approaches can be utilized in combination with more traditional pain therapies by combining two distinct pain modulatory processes/therapies. The knowledge gained from this study will provide novel mechanistic insight to better develop and tailor cognitive therapeutic interventions to target multiple chronic pain conditions.

18. RISK/BENEFIT RATIO

This study has a low risk, and the potential benefits of the proposed study outweigh the risks in terms of overall reward. The knowledge to be gained significantly outweigh the low risks associated with this study. In light of the ongoing opioid epidemic and the new prescribing guidelines by the Center for Disease Control to employ non-opiate based therapies, the identification of the endogenous and physiological mechanisms supporting such therapies is timely and of paramount importance. One promising behavioral therapy is mindfulness-based meditation training. However, we still do not fully appreciate how mindfulness reduces chronic pain. The primary purpose of this proposed study is to determine if endogenous opioidergic systems are engaged by mindfulness meditation to reduce chronic low back pain. Inquiry into this work may inform how mindfulness meditation can act as effectively as leading prescribed opiates, providing an alternative non-pharmacological pain treatment option. Importantly, if we replicate our findings in healthy individuals (i.e., mindfulness-based analgesia is not opioidergically mediated), then the treatment of chronic pain may be more effective with mindfulness and more conventional therapies due to a lack of cross-tolerance with opiate based medications. Thus, the benefits significantly outweigh the low risks of this study.

19. EXPENSE TO PARTICIPANT

Patients will have to pay \$4 for parking for every visit to the ACTRI (3 visits to the ACTRI = \$12), and will be responsible for their own method of transportation.

20. COMPENSATION FOR PARTICIPATION

Participants will not be compensated for parking but will receive \$400.00 in pro-rated payments as compensation for participation in this research. Participants will be paid with Vanilla Visa Gift Cards after each attended study session. They will be paid \$40 for each experimental session that pain evoking procedures are used (3 sessions = \$120). For each mindfulness session, they will be

compensated \$10 (4 sessions = \$40). For each session where naloxone/saline is administered, they will be compensated \$80 (2 sessions = \$160). And upon study completion, they will also receive an additional \$80 for successfully completing all study sessions.

We believe that the modest stipend of \$400 is appropriate without invoking coercion.

To receive payment, participants must provide their social security number, name and address in compliance with IRS (Internal Revenue Service) reporting requirements. When payments are reported to the IRS, the study team will not let them know what the payment is for, only that participants have been paid. If participants do not wish to provide this information, they can still take part in this study but will not be paid.

24. BIOLOGICAL MATERIALS TRANSFER AGREEMENT

Not applicable.

25. INVESTIGATIONAL DRUG FACT SHEET AND IND/IDE HOLDER

IND Exemption Form (attached)

26. IMPACT ON STAFF

Not applicable

27. CONFLICT OF INTEREST

The PI and all key personnel report no conflicts of interest.

28. SUPPLEMENTAL INSTRUCTIONS FOR CANCER-RELATED STUDIES

Not applicable

29. OTHER APPROVALS/REGULATED MATERIALS

Not applicable

30. PROCEDURES FOR SURROGATE CONSENT AND/OR DECISIONAL CAPACITY
ASSESSMENT
Not applicable

**Title:** Chronic Low Back Pain and Meditation

**NCT Record #:** NCT04034004

**Date:** May 3, 2023

**PI:** [name]

**Sample Size Determination:** Our targeted sample size is 60 cLBP patients (30/group). To conduct group comparisons among the two primary outcomes (naloxone + saline induced changes in pain ratings) and to ensure an overall type I error rate  $< 0.05$ , we used conservative Bonferroni corrections in all power calculations. Employing the pilot data corresponding to our previous work (Wells et al., 2020), we fit repeated measures ANOVA models that include indicator variables for group (mindfulness vs. non-mindfulness) and session (baseline vs. naloxone vs. saline). The estimated square root of mean square errors is 0.23 (23%) for pain ratings. Thirty subjects will provide 80% power to detect a pain rating difference of 22% between the naloxone and saline conditions in the non-mindfulness group with an estimated SD of 0.3 (30%). We expect no meaningful differences in pain reductions between naloxone and saline infusion during mindfulness meditation. Thus, we will have 80% power to detect a significant group X drug type interaction. Finally, 30 subjects/group will provide 80% power to detect a significant group difference of 19% for pain intensity. Such effect sizes parallel those observed in our pilot data (Wells et al., 2020).

#### Primary outcomes

- Numerical pain ratings while lying in the supine and in response to the straight leg raise test (SLR), respectively.

#### Secondary outcomes

- Brief Pain Inventory (BPI): interference and severity measures of chronic low back pain.
- Pain Catastrophizing Scale (PCS): This is a 13-item assessment derived from definitions of catastrophizing. The PCS yields a total score and three subscale scores assessing rumination, magnification, and helplessness in subjects.
- Roland-Morris Disability Questionnaire (RMDQ): This is a critical assessment for the chronic low back pain phenotype and was recommended for use by the NIH.
- PROMIS 29-Item Profile: This is a 29-item generic health-related survey that assesses the following 7 domains: depression, anxiety, physical function, pain interference, fatigue, sleep disturbance, and ability to participate in social roles/activities.

#### Exploratory outcome

- SF-12 Health Survey (SF-12): This is a 12-item version of the SF-36 item Health Survey designed to assess general mental and physical functioning, and overall health-related quality of life.

**Statistical Analysis Plan:** To test the primary hypotheses, a 2 (group) X 2 (rest vs. manipulation) X 3 (baseline vs. naloxone vs. saline) mixed model ANOVA will be employed to test differences in the change in pain from supine to straight leg raise test (SLR 1; SLR 2) within and across each testing session. Significant interactions will be explored using post-hoc paired simple effects tests to test the hypotheses that non-mindfulness meditation but not mindfulness induced analgesia will be reversed by administration of naloxone but not saline. Between group comparisons will also be explored with simple effects tests.

Secondary and exploratory outcomes will be assessed with a 2 (group) X 2 (baseline vs. post-intervention) by testing between and within group differences comparing baseline vs. post-study assessments. Simple effects tests will interpret significant main effects and interactions.

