Patients will return to the ACTRI to complete session 7 and will follow the same procedures (except for drug administration) as Session 6. Participants must wait 2 days to participate but no longer than 7 days to complete Session 7. Drug symptomology will be assessed after each session.

Primary Outcome Measure(s):

1. Visual Analog Scale (VAS) and numerical rating scales (NRS): Pain ratings (VAS pain intensity, VAS unpleasantness, and numerical pain ratings) will be assessed in response to the straight leg raise test.
2. exploratory outcomes include those corresponding to "heat induced pain ratings" (i.e. thermal stimulation), and lying supine. The minimum rating ("0") is designated as "no pain" whereas the maximum ("10") is labeled as "most intense imaginable" or "most unpleasant imaginable." Higher numbers correspond to higher pain.
 - a. We will collect naloxone and saline induced changes in pain intensity and pain unpleasantness ratings

Sample Size Determination: Our targeted sample size is 60 cLBP patients (30/group). To conduct group comparisons among the two primary outcomes (naloxone + saline induced changes in pain intensity + unpleasantness) and to ensure an overall type I error rate < 0.05, we used conservative Bonferroni corrections ($p = .025$) in all power calculations. Employing the pilot data corresponding to our previous work (Wells et al., 2020), we fit repeated measures ANOVA models that include indicator

variables for group (mindfulness vs. sham) and drug (naloxone vs. saline). The estimated square root of mean square errors is 0.23 (23%) and 0.30 (30%) for pain intensity and pain unpleasantness, respectively. Thirty subjects will provide 80% power to detect a pain rating difference of 22% between the naloxone and saline conditions in the non-mindfulness group with an estimated SD of 0.3 (30%). We expect no meaningful differences in pain reductions between naloxone and saline infusion during mindfulness meditation. Thus, we will have 80% power to detect a significant group X drug type interaction. Finally, 30 subjects/group will provide 80% power to detect a significant group difference of 19% for pain intensity and 24% for pain unpleasantness. Such effect sizes parallel those observed in our pilot data (Wells et al., 2020). Statistical power will be also greater when pre-regimen pain ratings are entered as covariates to reduce residual variance.

Questionnaires for Study Assessments:

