Drug Administration: All studies will be conducted with the supervision of ACTRI nurses in the ACTRI. As previously conducted (Zeidan, Adler-Neal et al. 2016), a 0.15mg/kg bolus dose of naloxone (Naloxone HCl, Amphastar Pharmaceuticals) or 25ml of normal saline will be administered over 10 minutes via the IV line of the antecubital vein of the non-dominant arm. Onset of naloxone-induced opioidergic antagonism occurs within 2 min of infusion and exhibits an average half-life of 64 min (Ngai, Berkowitz et al. 1976). To further ensure that naloxone will antagonize opioid receptors for the study entirety, we will administer a supplementary maintenance intravenous infusion dose of 0.15 mg/kg/h naloxone or saline immediately after bolus infusion ceases. The duration of the study from the onset of IV infusion to completion will be no more than 25 (average time of infusion = approx. 15 minutes). Only the study physicians, research pharmacist, and study coordinator will be aware of participant drug assignment.

Sample Size Determination & Power:

Assuming a conservative 20% dropout rate, we will recruit and randomize a total of 74 cLBP patients (n=37/group) to a mindfulness meditation or non-mindfulness meditation regimen. To conduct group comparisons among the two primary outcomes (naloxone + saline induced changes in pain intensity + unpleasantness) and to ensure an overall type I error rate < 0.05, we used conservative Bonferroni corrections (p= .025) in all power calculations. Employing the pilot data corresponding to preliminary findings and our previous work [22], we fit repeated measures ANOVA models that include indicator variables for group (mindfulness vs. non-mindfulness), drug (naloxone vs. saline), and session order. The estimated square root of mean square errors is 0.23 and 0.30 for pain intensity and pain unpleasantness, respectively. Thirty participants per group will provide 80% power to detect a group difference of 0.19 for pain intensity and 0.24 for pain unpleasantness. Such effect sizes are consistent with those observed from our pilot data. Statistical power will be also greater when pre-regimen pain ratings are entered as covariates to reduce residual variance.

Data Analyses and Interpretation:

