Primary Outcome: Age and sex will be entered as covariates in all appropriate analyses if between group differences exist. To test study hypotheses, a 2 (group) X 2 (rest vs. manipulation) X 3 (naloxone vs. saline) repeated measures (RM) ANOVA will be employed. Post-hoc paired samples t-tests (in each group) will be conducted to test the hypotheses that non-mindfulness meditation but not mindfulness induced analgesia will be reversed by administration of naloxone but not saline.

Exploratory analyses may be conducted (in supplementary papers) on the psychological assessments (Questionnaires for Study Assessments) to better appreciate the relationship in dispositional pain and the potential changes in pain responses due to the respective interventions.

Inclusion of Women and Minorities: Participants will include all sexes and races. We plan to screen from over 2500 cLBP patients from the ACTRI's pain recruitment service, 11 separate providers, and the local community. Based on the latest San Diego-based demographic consensus, we plan to recruit 60% White, 16% Asian, 7% Black, 0.5% Native American, 0.5% Pacific Islander, 12% Other race, 5% two or more races (We expect that 29% of our participants will be Hispanic or Latino). If necessary to obtain minority representation, under-represented racial groups will be targeted specifically for recruitment.

General Considerations:

Data for all individual participants randomized or exposed to study drug will be presented in data listings. Continuous data will be summarized using the following descriptive summary statistics: the number of subjects (n), mean, SD, SE, median, minimum value (min), and maximum value (max). Categorical data will be summarized using counts and percentages.

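### The SAP claims power for the group x (naloxone vs saline) interaction but does not make it the confirmatory test of reversal or give it an alpha; the hypothesis goes to paired tests within each group

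*SAP*

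**What the plan says.** The SAP's Statistical Analysis Plan paragraph (printed under Exploratory outcome) states that "a 2 (group) X 2 (rest vs. manipulation) X 3 (baseline vs. naloxone vs. saline) mixed model ANOVA will be employed", applied to the change in pain from supine to straight leg raise. It continues: "Significant interactions will be explored using post-hoc paired simple effects tests to test the hypotheses" that control but not mindfulness analgesia is reversed by naloxone. It does not say which interaction counts, does not define a naloxone-versus-saline contrast and gives no alpha.

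The SAP's Sample Size Determination takes a 22% naloxone-saline difference in controls and none in mindfulness, and concludes: "Thus, we will have 80% power to detect a significant group X drug type interaction". Its power model has a three-level factor, "session (baseline vs. naloxone vs. saline"). It mentions Bonferroni correction without a value.

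The Protocol (section 9) has two sample-size paragraphs, both with a planning alpha of .025. One models "variables for group (mindfulness vs. sham) and drug (naloxone vs. saline"). The other models "drug (naloxone vs. saline), and session order". Its analysis paragraph (Primary Outcome) plans a "2 (group) X 2 (rest vs. manipulation) X 3 (naloxone vs. saline) repeated measures (RM) ANOVA will be employed", which gives three levels but names two, and adds: "Post-hoc paired samples t-tests (in each group) will be conducted to test the hypotheses".

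The Protocol presents Session 1 as the baseline behavioural control and places randomisation after it, so the baseline level appears to precede both randomisation and training.

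**The concern.** The hypothesis concerns a difference between groups: is naloxone minus saline larger in controls than in mindfulness? That is one degree of freedom. The plan instead tests naloxone against saline in each group separately and would read one significant and one non-significant result as the answer. Two groups with the same true effect can easily produce that pattern by chance.

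The interaction gate gives limited protection. The three-way term covers three sessions, so it can be significant because mindfulness training lowers pain under both infusions, with no difference in reversal. The SAP also does not restrict which interaction opens the paired tests. The trial's central mechanistic conclusion, that control relief is opioid-mediated and mindfulness relief is not, could then rest on a comparison that was never tested.

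**Working it through.** **Inputs from the documents.** 30 per group; naloxone effect 0.22 in controls and 0 in mindfulness; SD 0.30, not said to be per condition or of the paired difference; root MSE 0.23 (intensity) and 0.30 (unpleasantness); group differences 0.19 and 0.24; planning alpha .025 (Protocol). **Assumed:** two-sided tests, normal data, equal between-session correlation of 0 to 0.5, and SD of the within-session change 0.23 to 0.30.

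**1. The plan's group-difference figures.** Noncentrality = difference / (SD x sqrt(2/30)), 58 df, alpha .025.
- Intensity: 0.19 / (0.23 x 0.2582) = 3.20, power 81.3%.
- Unpleasantness: 0.24 / (0.30 x 0.2582) = 3.10, power 78.5%.

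Both agree with the stated 80%.

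**2. The plan's interaction figure.** The contrast is 0.22 - 0 = 0.22. It compares each person's naloxone-minus-saline difference between groups.
- If 0.30 is the SD of the paired difference: 0.22 / (0.30 x 0.2582) = 2.84. Power is 70% at .025 and 80% at .05. The control simple effect is then 0.22 / (0.30 / sqrt(30)) = 4.02, power 97% at .05.
- If 0.30 is per condition with correlation 0, the SD of the difference is 0.30 x sqrt(2) = 0.424: 0.22 / (0.424 x 0.2582) = 2.01. Power is 39% at .025 and 51% at .05. The control simple effect is 0.22 / (0.424 / sqrt(30)) = 2.84, power 78% at .05.

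No single reading gives 80% for both the simple effect and the interaction, so the second does not follow from the first. With SD of the paired difference = SD x sqrt(2(1 - correlation)), the assumed grid gives interaction power of 39-92% at .025 and 51-95% at .05.

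**3. False finding of reversal in controls only, no gate.** If both groups have the same effect and each paired test has power p, the pattern occurs with probability p(1 - p), at most 25%. For an equal effect of 0.10 at alpha .025 (29 df):
- SD of difference 0.23: noncentrality 0.10 x sqrt(30) / 0.23 = 2.38, p = 0.515, pattern 0.515 x 0.485 = 25%.
- SD of difference 0.424: noncentrality 1.29, p = 0.157, pattern 0.157 x 0.843 = 13%.

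For an equal effect of 0.22, p is 0.997 and 0.683 at the same two ends, giving 0.3% and 22%.

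**4. The same pattern behind a gate.** Simulation, 20,000 trials per cell, alpha .025, F(2,116) for the session terms on the within-session change. The pattern requires controls significant with naloxone worse, and mindfulness not significant.
- Equal effect 0.10, mindfulness better by 0.19 in both infusion sessions: three-way gate 5-22%; gate on the 1-df contrast about 1%.
- Equal effect 0.10, no group difference: three-way gate about 1%; three-way or manipulation x session 9-24%.
- Equal effect 0.22, group difference 0.19: three-way gate 0.3-8%.
- No naloxone effect, group difference 0.19: the three-way term is significant in 31-86% of trials, but the false pattern occurs in only about 1%, gated or not.

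**The case against.** The target can be identified from the documents. The sample-size text names the interaction, gives the expected pattern and claims power for it; the planned ANOVA can estimate it; and the Protocol supplies a planning alpha. A reader might infer that the interaction was never planned, and the documents do not support that. What is missing is its status as the deciding test, and its alpha.

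A reader might also infer that the Protocol's paired t-tests are definitely ungated. The label post-hoc, directly after the ANOVA, can be read as requiring a significant ANOVA first, so the 13-25% belongs to one reading only.

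Conversely, one might say the SAP's gate protects unless the groups differ in both infusion sessions. That holds only if the three-way term is the sole gate. The SAP says significant interactions without restriction, and the 9-24% shows what that allows.

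The equal effect of 0.10 is chosen near the worst case, and the SD of the change and the correlations are assumed. This stands. It limits the magnitudes but does not affect the logic.

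**Conclusion.** The concern holds. A between-group hypothesis is assigned to within-group tests, and no passage makes the group x (naloxone vs saline) contrast confirmatory or gives it an alpha. The logic is firm. The size depends on which interaction opens the paired tests and on values the documents do not give. The risk is material when naloxone has a moderate effect shared by both groups. At the plan's own 0.22 it spans 0.3% to 22% across the three-way gate and no gate.

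A reader might infer that including baseline by itself produces false reversal findings. It does not: without a naloxone effect the rate is about 1%, even though the three-way term is often significant.

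The claimed 80% interaction power is reached only at two-sided .05 with 0.30 read as the SD of the paired difference, or under more favourable assumed SDs and correlations. This should be fixed, but it does not call for redesign.

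**What to change.** In the SAP's Statistical Analysis Plan:
- Name the 1-df contrast group x (naloxone vs saline), on the SAP's own supine-to-leg-raise change in Sessions 6 and 7, as the confirmatory test of reversal. In the full model this is group x manipulation x (naloxone vs saline).
- State its alpha: .025 if two primary pain outcomes are kept, .05 if one.
- Include the session-order term that one of the Protocol's power models already has.
- Use the paired tests only to describe a significant contrast, and keep the 2 x 2 x 3 ANOVA as supportive.
- Define SLR 1, SLR 2 and the supine rating paired with each. The documents do not define them, so this is a question for the authors and not grounds for substituting SLR 2 minus SLR 1.

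In the Protocol's Primary Outcome paragraph, correct the factor that states three levels and names two. In the SAP's Sample Size Determination, restate the interaction power, saying what the SD of 0.30 refers to and which correlation and alpha were used.

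Cost: no new data, visits or patients. The contrast is a harder test, the stated power becomes less favourable on most readings, and the comparison with baseline becomes supportive.

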Non-mindfulness Meditation Training: The main purpose of the non-mindfulness meditation regimen is to serve as an active control for a crucial, essential element of mindfulness meditation (i.e., mindful attention to breath and non-reactivity to sensory events)(Zeidan, Johnson et al. 2010, Zeidan, Emerson et al. 2015). This regimen is designed so that the primary difference between the mindfulness and non-mindfulness meditation training is the mindfulness meditation group’s explicit mindfulness-based instructions (e.g., mindful attention to the breath). The non-mindfulness meditation group will be told that they are randomly assigned to the meditation group (Zeidan, Johnson et al. 2010, Zeidan, Emerson et al. 2015). In each of the four 20-minute training sessions, participants will be instructed to close their eyes, and to take a deep breath “as we sit here in meditation” every 2-3 minutes (Zeidan, Johnson et al. 2010, Zeidan, Emerson et al. 2015). All other aspects (training room, posture, facilitator, time providing instruction) of the non-mindfulness meditation intervention will be matched.

Sessions 6 & 7: Post-Regimen Session: We will employ a double-blinded crossover design to correspond to the administration of the opioid antagonist, naloxone and placebo-saline across two separate sessions at UCSD’s Altman Clinical and Translational Research Institute (ACTRI). A total of 30 subjects in each group will receive naloxone in Session 6 and saline in Session 7. Conversely, the other 30 subjects in each group will receive saline in Session 6 and naloxone in Session 7. After successful completion of their respective regimen, participants will report to the ACTRI. A research technician will greet patients as they arrive to the ACTRI and guide them to the clinic room. Next, the research technician will issue study assessments to the participant. ACTRI nurses will then administer an opiate-focused urine drug screening to confirm that no participants are using opioids to remove the risk of opioid withdrawal symptoms during naloxone administration, and a pregnancy test (if applicable). Weight will be subsequently measured to confirm the prescribed drug dosage. Next, the

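### Secondary and exploratory scales: the 2 x 2 analysis leaves out baseline adjustment and lets a shared time effect open within-group tests, with no between-group contrast named as decisive

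*SAP*

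**What the plan says.** The last part of the SAP, headed Statistical Analysis Plan, gives two sentences to these outcomes. The first sets the model: "Secondary and exploratory outcomes will be assessed with a 2 (group) X 2 (baseline vs. post-intervention) by testing between and within group differences". The second sets the follow-up: "Simple effects tests will interpret significant main effects and interactions". The factors are group and time. No covariate is named, and no sentence says which term decides whether training had an effect.

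For the primary outcome, the same part of the SAP ties its paired tests to interactions: "Significant interactions will be explored using post-hoc paired simple effects tests". It adds that between-group comparisons will be explored as well.

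Covariates appear only in Protocol section 9. The power text says: "Statistical power will be also greater when pre-regimen pain ratings are entered as covariates to reduce residual variance". That concerns pain ratings, and the SAP does not carry it over to any outcome. Under Data Analyses and Interpretation, in the paragraph on the primary outcome, the Protocol says: "Age and sex will be entered as covariates in all appropriate analyses if between group differences exist". This is conditional and does not adjust for the baseline score.

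The SAP sentence calls the second time point *post-intervention* and then *post-study*: "by testing between and within group differences comparing baseline vs. post-study assessments". For Session 6, Protocol section 9 says: "Next, the research technician will issue study assessments to the participant". That step precedes the infusion, and Session 7 repeats the procedures. Neither description lists the scales given.

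**The concern.** In a two-group pre/post design only the group x time term isolates the training effect. The time main effect says that participants changed on average. The group main effect averages the post score with a pre-randomisation score, so a true effect of size δ appears in it as δ/2.

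Under the stated rule a significant time main effect is enough to trigger simple effects tests, and these include a baseline-to-post test in each group. Such tests can easily be significant in one group and not in the other when both groups changed by the same amount.

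Shared improvement is plausible here. The control is an active regimen whose participants are told that they are receiving mindfulness meditation, and entry requires pain of at least 3 out of 10, which invites some regression to the mean.

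Two things are at stake: a possible claim that mindfulness improved disability or catastrophizing and the control did not, without evidence of a group difference; and precision that the baseline scores would supply at no cost.

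**Working it through.** **The plan's own figure.** The documents give no power for the secondary scales. The nearest stated figure is 80% power for a 19% group difference in pain intensity. With SD 0.23, 30 per group and two-sided 0.025, a two-sample t-test gives 81.3%, so the figure reproduces. It does not bear on this point.

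**Inputs.** From the SAP: 30 per group, 2 x 2 model, simple effects after main effects or interactions. Assumed, because the documents do not say: tests at two-sided 0.05, equal SD at baseline and post, baseline-post correlation ρ, and the size of the shared improvement. The model is read as a mixed ANOVA.

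**Step 1: precision.** In units of SD², the group x time test compares change scores with variance 2(1 − ρ). ANCOVA on the baseline score has residual variance 1 − ρ². The ratio is (1 − ρ²) / [2(1 − ρ)] = (1 + ρ)/2, ignoring the small cost of estimating the slope.

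| ρ | Variance ratio | SE of change test relative to ANCOVA | Difference detectable with 80% power, SD units: ANCOVA / change | Power at 0.5 SD: ANCOVA / change |
|---|---|---|---|---|
| 0.3 | 0.65 | 1.24 | 0.69 / 0.86 | 53% / 37% |
| 0.5 | 0.75 | 1.15 | 0.63 / 0.72 | 61% / 49% |
| 0.7 | 0.85 | 1.08 | 0.52 / 0.56 | 77% / 71% |
| 0.9 | 0.95 | 1.03 | 0.315 / 0.323 | 99.3% / 99.1% |

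Detectable difference = √variance × √(2/30) × (1.96 + 0.84). At ρ = 0.5 the gain equals having 1/0.75 = 1.33 times the participants.

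**Step 2: what the main-effect rule lets through.** Both groups improve by the same amount and there is no group difference. A simulation of 200,000 trials per scenario applied the stated rule: time or interaction significant, then a paired test within each group.

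| ρ | Shared improvement | Time effect significant | Mindfulness within-group test significant | Mindfulness significant, control not (after the rule) | Interaction significant |
|---|---|---|---|---|---|
| 0.5 | 0.3 SD | 63% | 36% | 20.5% | 5% |
| 0.5 | 0.4 SD | 86% | 56% | 23.5% | 5% |
| 0.5 | 0.5 SD | 97% | 75% | 18.3% | 5% |
| 0.7 | 0.3 SD | 84% | 54% | 23.5% | 5% |
| 0.7 | 0.4 SD | 98% | 78% | 17.0% | 5% |
| 0.7 | 0.5 SD | 99.8% | 93% | 6.7% | 5% |

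**Hand check.** The groups are independent, so without the rule the mindfulness-only pattern has probability p(1 − p), where p is the power of one within-group test. At ρ = 0.5 and 0.4 SD, 0.564 × 0.436 = 24.6%, against 23.5% after the rule. At ρ = 0.7 and 0.5 SD, 0.928 × 0.072 = 6.7%. The rule removes little, because the time effect is nearly always significant when within-group tests have reasonable power.

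**Step 3: the comparator.** The 5% for the interaction counts both directions. By symmetry, about 5%/2 = 2.5% would favour mindfulness.

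**The case against.** The strongest reply is that the 2 x 2 model already contains group x time, which is a valid and unbiased test under randomisation, and that the SAP sets out to test between-group as well as within-group differences. This stands. A reader might infer that the plan will treat a within-group p-value as proof of a mindfulness effect. No sentence says so, and a time main effect on its own means that participants changed on average, whichever group they were in. The misreading is a risk that the wording leaves open.

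A reader might also infer that half of all trials would produce the misleading pattern, since 2 × 0.5 × 0.5 = 50%. That counts a result in either group alone and takes p = 0.5, where the expression peaks. In the direction that matters the ceiling is 0.5 × 0.5 = 25%.

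On precision, the gain depends on a correlation that the documents do not give. The whole study must be completed within 40 days. If the scales are stable over that time, the correlation is high and the gain is small. That is fair: baseline adjustment here is a matter of efficiency, and the change-score test is not biased.

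The scales might be taken for the trial's only clinical outcomes. The documents contradict that: supine pain is a primary outcome in the SAP, SF-12 is exploratory, and Protocol section 9 lists further clinical questionnaires. The trial's objective is mechanistic (Protocol section 6), and section 13 says that it is not a treatment study. This limits the weight of the point but does not remove it, because the SAP names four of these scales as secondary outcomes.

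Finally, it is tempting to assume a pre-infusion Session 6 score on every scale. The Protocol says only that assessments are issued then, so the sponsor has to confirm which ones.

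**Conclusion.** The concern holds in a limited form. The SAP's rule for the secondary and exploratory scales leaves out baseline adjustment, does not make the between-group contrast decisive, and lets a time effect shared by both groups open within-group tests. If both groups improve equally by 0.3 to 0.5 SD, mindfulness alone is significant in roughly 18-24% of trials per scale at ρ = 0.5 and 7-24% at ρ = 0.7, against 5% for a false interaction. The unadjusted contrast gives up between 35% of the variance (ρ = 0.3) and 5% (ρ = 0.9). These figures rest on assumed values for the correlation, the shared improvement and a two-sided 0.05 level.

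The pattern can recur over about 14 secondary scores (BPI 2, PCS 4, RMDQ 1, PROMIS-29 7), which are correlated with one another, and again for SF-12. The post time point is not uniquely defined, and a Session 7 score would follow an earlier infusion and pain testing. The change is worth making. It does not touch the primary analysis.

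**What to change.** For each secondary and exploratory scale, replace the 2 x 2 test with an ANCOVA of the post score on group and the Session 1 score. A mixed model that constrains the two groups to a common baseline mean would serve equally well. State that the adjusted group difference with its 95% CI is the sole basis for any statement about a mindfulness effect.

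Report within-group changes descriptively, and remove the provision that a time main effect opens tests.

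Name one post time point in place of the two labels now used. The Session 6 pre-infusion score is preferable if the sponsor confirms that these scales are collected then, with Session 7 scores as a sensitivity analysis.

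The cost is SAP wording; no new data are needed if collection at the chosen time point is confirmed. The one small loss is that within-group p-values are no longer reported as evidence. The change does not by itself control multiplicity across the scales. The SAP's only statement on that concerns the two primary outcomes in the power calculations.
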